# **3 STUDY OBJECTIVES AND ENDPOINTS.**

#### Table 3-1 Study Objectives and Endpoints

Objectives	Endpoints
Primary	·
To determine the clinical efficacy of a 0.454% w/w SnF 2 toothpaste in reducing DH to an evaporative (air) stimulus (as measured by Schiff sensitivity score), compared to a negative control toothpaste, after 12 weeks twice daily use.	Change from Baseline in Schiff sensitivity score at Week 12.
Secondary	
To determine the clinical efficacy of a $0.454\%$ w/w SnF 2 toothpaste in reducing DH to a tactile stimulus (as measured by tactile threshold), compared to a negative control toothpaste, after 12 weeks twice daily use.	Change from Baseline in tactile threshold (grams [g]) at Week 12.
To determine the clinical efficacy of a 0.454% w/w SnF 2 toothpaste in reducing DH to an evaporative (air) stimulus (as measured by Visual Analogue Scale [VAS]), compared to a negative control toothpaste, after 12 weeks twice daily use.	Change from Baseline in VAS (millimeters [mm]) at Week 12.
To determine the clinical efficacy of a $0.454\%$ w/w SnF 2 toothpaste in reducing DH to evaporative (air) and tactile stimuli (as measured by Schiff sensitivity score/VAS and tactile threshold, respectively), compared to a negative control toothpaste, after 6 weeks twice daily use.	Change from Baseline in Schiff sensitivity score, tactile threshold (g) and VAS (mm) at Week 6.
To determine the clinical efficacy of a 5.0% w/w calcium sodium phosphosilicate (CSPS) toothpaste (positive control) in reducing DH to evaporative (air) and tactile stimuli (as measured by Schiff sensitivity score/VAS and tactile threshold, respectively), compared to a negative control toothpaste, after 6 and 12 weeks twice daily use.	Change from Baseline in Schiff sensitivity score and tactile threshold (g) and VAS (mm) at Week 6 and Week 12.
Safety	
To evaluate the safety and oral tolerability of the study toothpastes when used twice daily for 12 weeks.	Treatment emergent adverse events (TEAEs)

The study will be considered successful if the 0.454% SnF2 toothpaste demonstrates statistically significant, superior anti-hypersensitivity efficacy, compared to negative control, as measured by Schiff sensitivity score at Week 12.

Property of GSK Consumer Healthcare - Confidential

May not be used, divulged, published or otherwise disclosed without the consent of GSKCH

CCI

Clinical Protocol Template v9.0

Page 16 of 73

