## 12 STATISTICAL CONSIDERATIONS AND DATA ANALYSES

## 12.1 Sample Size Determination

CCI

Sufficient subjects will be screened to randomize approximately 240 subjects to study treatment to ensure approximately 235 complete the study (approximately 94 subjects each for test toothpaste and negative control, and 47 subjects for positive control), allowing for 2% dropouts after randomization, as observed in previous clinical studies conducted in China.

The study will be powered sufficiently to demonstrate statistical superiority of the test toothpaste compared to the negative control for the change from Baseline in the Schiff sensitivity score after 12 weeks of treatment.

The true effect size is expected to be 0.5 (effect size (ES) = mean difference [test toothpaste – negative control] / pooled standard deviation [SD]; mean difference = 0.3, SD=0.6). Such assumptions would also infer at least a 15% superior relative mean change from Baseline for the test toothpaste compared to the negative control (assuming mean change from a Baseline Schiff sensitivity score for negative control less than 2), a requirement of the Chinese MoH guidelines for the testing of functional (desensitising) toothpastes for at least one clinical DH measure (Ministry of Health (China), 2010).

Property of GSK Consumer Healthcare - Confidential

May not be used, divulged, published or otherwise disclosed without the consent of GSKCH

Clinical Protocol Template v9.0

Page 57 of 73

With 94 subjects per group (for test toothpaste and negative control arms), there is 92.65% power to detect an effect size of 0.5 at the two-sided 5% significance level based on a two-sample t-test (using PASS software version 19.0.1).

Estimates of the above dropout rate and SD are based on results from three similar clinical studies (sponsor clinical studies: 205794, 208153, 216954).

The positive control has clinically proven longer-term DH efficacy in two clinical studies conducted in China on Chinese populations (sponsor clinical studies: CCl which satisfied the China MoH requirements (Ministry of Health (China), 2010). As such, it has been included in this study as a benchmark of performance in the Chinese population for

'study validation'; 47 subjects in the positive control group are deemed sufficient to demonstrate statistical superiority for positive vs. negative controls.

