#### Table 1-2 Study Objectives and Endpoints

Objectives	Endpoints		
Primary Objective	Primary Endpoint		
To determine the clinical efficacy of a 0.454% w/w SnF 2 toothpaste in reducing DH to an evaporative (air) stimulus (as measured by	Change from Baseline in Schiff sensitivity score at Week 12.		
GlaxoSmithKline Consumer Healthcare Confidential			

GlaxoSimunKime Consumer Healthcare Confidential

Statistical Analysis Plan Template v6.0

Page 9 of 36

Objectives	Endpoints
Schiff sensitivity score), compared to a	
negative control toothpaste, after 12 weeks	
twice daily use.	
Secondary Objectives	Secondary Endpoints
Efficacy	
To determine the clinical efficacy of a 0.454% w/w SnF 2 toothpaste in reducing DH to a tactile stimulus (as measured by tactile threshold), compared to a negative control toothpaste, after 12 weeks twice daily use.	Change from Baseline in tactile threshold (grams [g]) at Week 12.
To determine the clinical efficacy of a 0.454% w/w SnF 2 toothpaste in reducing DH to an evaporative (air) stimulus (as measured by Visual Analogue Scale [VAS]), compared to a negative control toothpaste, after 12 weeks twice daily use.	Change from Baseline in VAS (millimeters [mm]) at Week 12.
To determine the clinical efficacy of a 0.454% w/w SnF 2 toothpaste in reducing DH to evaporative (air) and tactile stimuli (as measured by Schiff sensitivity score/VAS and tactile threshold, respectively), compared to a negative control toothpaste, after 6 weeks twice daily use.	Change from Baseline in Schiff sensitivity score, tactile threshold (g) and VAS (mm) at Week 6.
To determine the clinical efficacy of a 5.0% w/w calcium sodium phosphosilicate (CSPS) toothpaste (positive control) in reducing DH to evaporative (air) and tactile stimuli (as measured by Schiff sensitivity score/VAS and tactile threshold, respectively), compared to a negative control toothpaste, after 6 and 12 weeks twice daily use.	Change from Baseline in Schiff sensitivity score and tactile threshold (g) and VAS (mm) at Week 6 and Week 12.
Safety	
To evaluate the safety and oral tolerability of the study toothpastes when used twice daily for 12 weeks.	Treatment emergent adverse events (TEAEs)

This study will be considered successful if there is a statistically significant difference between 0.454% SnF2 and negative control by the primary efficacy variable, change from Baseline in Schiff sensitivity score at week 12.

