## 1.4 Sample Size Calculation

Sufficient subjects will be screened to randomize approximately 240 subjects to study treatment to ensure approximately 235 complete the study (approximately 94 subjects each for test toothpaste and negative control, and 47 subjects for positive control), allowing for 2% dropouts after randomization, as observed in previous clinical studies conducted in China.

The study will be powered sufficiently to demonstrate statistical superiority of the test toothpaste compared to the negative control for the change from Baseline in the Schiff sensitivity score after 12 weeks of treatment.

GlaxoSmithKline Consumer Healthcare Confidential Statistical Analysis Plan Template v6.0 Page 11 of 36

The true effect size is expected to be 0.5 (effect size (ES) = mean difference [test toothpaste – negative control] / pooled standard deviation [SD]; mean difference = 0.3, SD = 0.6). Such assumptions would also infer at least a 15% superior relative mean change from Baseline for the test toothpaste compared to the negative control (assuming mean change from a Baseline Schiff sensitivity score for negative control less than 2), a requirement of the Chinese MoH guidelines for the testing of functional (desensitising) toothpastes for at least one clinical DH measure (Ministry of Health (China), 2010).

With 94 subjects per group (for test toothpaste and negative control arms), there is 92.65% power to detect an effect size of 0.5 at the two-sided 5% significance level based on a two-sample t-test (using PASS software version 19.0.1).

Estimates of the above dropout rate and SD are based on results from three similar clinical studies (sponsor clinical studies: 205794, 208153, 216954).

The positive control has clinically proven longer-term DH efficacy in two clinical studies conducted in China on Chinese populations (sponsor clinical studies: **CC**) which satisfied the China MoH requirements (Ministry of Health (China), 2010). As such, it has been included in this study as a benchmark of performance in the Chinese population for 'study validation'; 47 subjects in the positive control group are deemed sufficient to demonstrate statistical superiority for positive vs. negative controls.

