## 4.4.1.2 Statistical Hypothesis, Model, and Method of Analysis

The primary comparison is between the test toothpaste and the negative control in the mITT population. As there is only a single primary objective no adjustment for multiple comparisons is required.

Study product differences will be tested under the null hypothesis at Week 12:

- H0: there is no difference between test product and negative control;
- H1: there is a difference between test product and negative control;

GlaxoSmithKline Consumer Healthcare Confidential Statistical Analysis Plan Template v6.0 Page 18 of 36

Change from Baseline in Schiff sensitivity score will be analyzed using a Mixed Model with Repeated Measures (MMRM), with study product, visit and study product by visit interaction as fixed effects, and Baseline Schiff sensitivity score as a covariate. Subject will be included as a repeated measure with unstructured covariance matrix. Kenward Rogers degrees of freedom approach will be applied (Kenward and Roger, 1997). If the model with unstructured covariance matrix does not converge then compound symmetry covariance matrix will be used.

Using the above model, adjusted mean change from Baseline, along with 95% confidence intervals (CIs) will be reported by study product. P-values testing for non-zero change from Baseline will be presented for all study products. Mean difference between study products at Week 12 (test toothpaste compared to negative control), 95% CIs and p-values will be provided for Schiff sensitivity score in Table 14.2.2.1.2. Significance testing will be conducted at the two-sided 5% significance level.

The assumption of normality and homogeneity of variance in the MMRM will be investigated. In case of violation of these assumptions, a suitable non-parametric test (the Van Elteren test, adjusted for the randomization stratification) will be performed to assess change from Baseline comparisons (test toothpaste vs. negative control at Week 12) and the results will be provided to support the MMRM results. The non-parametric results will be considered confirmatory under the observation of strong violations of the assumptions.

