## 4.4.2.2.1 Statistical Hypothesis, Model and Method of Analysis

Two comparisons will be considered for this secondary endpoint. Firstly, the comparison between the test toothpaste and the negative control in the mITT population. Secondly, the comparison between the positive control and the negative control in the mITT population.

- 1. Study product differences will be tested under the null hypothesis at Week 6 and Week 12:
- H0: there is no difference between test product and negative control;
- H1: there is a difference between test product and negative control;
- 2. Study product differences will be tested under the null hypothesis at Week 6 and Week 12:
- H0: there is no difference between positive control and negative control;
- H1: there is a difference between positive control and negative control;

GlaxoSmithKline Consumer Healthcare Confidential Statistical Analysis Plan Template v6.0 Page **21** of **36** 

Change from Baseline in tactile threshold (g) will be analyzed using the same MMRM as the primary endpoint but with Baseline tactile threshold (g) as a covariate, rather than Baseline Schiff sensitivity score. In addition, the maximum Baseline Schiff sensitivity score of the two test teeth (2 or 3) will be fitted as a fixed effect.

Using the above model, adjusted mean change from Baseline, along with 95% CIs will be reported by study product. P-values testing for non-zero change from Baseline will be presented for both study products. Mean difference between study products, 95% CIs and p-values will be provided for Tactile Threshold (g) score in Table 14.2.3.1.2. Significance testing will be conducted at the two-sided 5% significance level.

The assumption of normality and homogeneity of variance in the MMRM will be investigated. In case of violation of these assumptions, a suitable non-parametric test (the Van Elteren test, adjusted for the randomization stratification) will be performed to assess change from Baseline comparisons (test toothpaste vs. negative control and positive control vs. negative control at Weeks 6 and 12) and the results will be provided to support the MMRM results; the non-parametric results will be considered to supersede the MMRM results under the observation of strong violations of the assumptions.

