## 4.4.2.3.1 Statistical Hypothesis, Model and Method of Analysis

Two comparisons will be considered for this secondary endpoint. Firstly, the comparison between the test toothpaste and the negative control in the mITT population. Secondly, the comparison between the positive control and the negative control in the mITT population.

- 1. Study product differences will be tested under the null hypothesis at Week 6 and Week 12:
- H0: there is no difference between test product and negative control;
- H1: there is a difference between test product and negative control;
- 2. Study product differences will be tested under the null hypothesis at Week 6 and Week 12:
- H0: there is no difference between positive control and negative control;
- H1: there is a difference between positive control and negative control;

Change from Baseline in VAS (mm) will be analyzed using the same MMRM as mentioned in Section 4.4.2.2.1 but with Baseline VAS (mm) as a covariate, rather than the Baseline tactile threshold (g).

Using the above model, adjusted mean change from Baseline, along with 95% CIs will be reported by study product. P-values testing for non-zero change from Baseline will be presented for both study products. Mean difference between study products, 95% CIs and p-values will be provided for VAS (mm) score in Table 14.2.4.1.2. Significance testing will be conducted at the two-sided 5% significance level.

The assumption of normality and homogeneity of variance in the MMRM will be investigated. In case of violation of these assumptions, a suitable non-parametric test (the Van Elteren test, adjusted for the randomization stratification) will be performed to assess change from Baseline comparisons (test toothpaste vs. negative control and positive control vs. negative control at Weeks 6 and 12) and the results will be provided to support the MMRM results; the

> GlaxoSmithKline Consumer Healthcare Confidential Statistical Analysis Plan Template v6.0 Page 23 of 36

non-parametric results will be considered to supersede the MMRM results under the observation of strong violations of the assumptions.

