# Appendix 1: List of Data Displays

CSR Section	TLF	Number	Title	Population	Template	Topline
14.1 Demogra	phic Data Sur	mmary Tables	s and Figures	· ·		
	Table	14.1.1	Subject Disposition	All Screened Subjects	14.1.1	Yes
	Table	14.1.2	Incidence of Important Protocol Deviations	All Randomized Subjects	14.1.2	
	Table	14.1.3.1	Demographic and Baseline Characteristics	Safety Population	14.1.3.1	
	Table	14.1.3.2	Demographic and Baseline Characteristics	mITT Population	14.1.3.1	Yes
	Table	14.1.3.3	Demographic and Baseline Characteristics	PP Population	14.1.3.1	
14.2 Efficacy I	Data Summar	y Tables and	Figures			
	Table	14.2.1.1	Summary of Compliance	mITT Population	14.2.1.1	
	Table	14.2.1.2	Summary of Supervised Brushing (Investigational Product)	mITT Population	14.2.1.2	
	Table	14.2.1.3	Summary of Supervised Brushing (Acclimatization Product)	mITT Population	14.2.1.3	
	Table	14.2.2.1.1	Summary of Schiff Sensitivity Score of the 2 Test Teeth	mITT Population	14.2.2.1.1	Yes

GlaxoSmithKline Consumer Healthcare Confidential

CCI Statistical Analysis Plan template v5.0

Page 28 of 36

CSR Section	TLF	Number	Title	Population	Template	Topline
	Table	14.2.2.1.2	Statistical Analysis of Change from Baseline in Schiff Sensitivity Score Over Time (MMRM)	mITT Population	14.2.2.1.2	Yes
	Table	14.2.2.1.3	Statistical Analysis of Change from Baseline in Schiff Sensitivity Score Over Time (ANCOVA Sensitivity Analyses)	mITT Population	14.2.2.1.3	
	Figure	14.2.2.1.4	Schiff Sensitivity Score by Visit and Study Product	mITT Population	14.2.2.1.4	
	Table	14.2.2.2.1	Summary of Schiff Sensitivity Score of the 2 Test Teeth	PP Population	14.2.2.1.1	
	Table	14.2.2.2.2	Statistical Analysis of Change from Baseline in Schiff Sensitivity Score Over Time (MMRM)	PP Population	14.2.2.1.2	
	Table	14.2.2.2.3	Statistical Analysis of Change from Baseline in Schiff Sensitivity Score Over Time (ANCOVA Sensitivity Analyses)	PP Population	14.2.2.1.3	
	Table	14.2.3.1.1	Summary of Tactile Threshold (g) of the 2 Test Teeth	mITT Population	14.2.2.1.1	Yes
	Table	14.2.3.1.2	Statistical Analysis of Change from Baseline in Tactile Threshold (g) Over Time (MMRM)	mITT Population	14.2.3.1.2	Yes

GlaxoSmithKline Consumer Healthcare Confidential

CCI Statistical Analysis Plan Template v6.0

Page 29 of 36

CSR Section	TLF	Number	Title	Population	Template	Topline
	Table	14.2.3.1.3	Statistical Analysis of Change from Baseline in Tactile Threshold (g) Over Time (ANCOVA Sensitivity Analyses)	mITT Population	14.2.3.1.3	

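### Should the SAP report and pre-specify how the guideline's 15% relative superiority will be judged?

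*Protocol*

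**What the plan says.** Protocol 12.1 and SAP 1.4 use the same planning text: mean difference 0.3, SD 0.6, effect size 0.5, 94 completers in each of the test and negative-control arms, and 92.65% power from a two-sided 5% two-sample t-test. Between the effect size and the power statement, SAP 1.4 adds: "Such assumptions would also infer at least a 15% superior relative mean change from Baseline for the test toothpaste compared to the negative control". A bracketed condition follows, that the negative-control mean change is below 2. The protocol describes the 15% as "a requirement of the Chinese MoH guidelines for the testing of functional (desensitising) toothpastes for at least one clinical DH measure".

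The 15% does not appear again. Protocol section 3 defines success as the test "toothpaste demonstrates statistically significant, superior anti-hypersensitivity efficacy, compared to negative control, as measured by Schiff sensitivity score at Week 12". SAP 1.2 likewise rests success on a significant difference "by the primary efficacy variable, change from Baseline in Schiff sensitivity score at week 12".

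For Schiff, SAP 4.4.1.2 plans adjusted mean changes by product with 95% CIs, and then: "Mean difference between study products at Week 12 (test toothpaste compared to negative control), 95% CIs and p-values will be provided". Tactile threshold (4.4.2.2.1: "Mean difference between study products, 95% CIs and p-values will be provided for Tactile Threshold (g) score in Table 14.2.3.1.2") and VAS (4.4.2.3.1: "Mean difference between study products, 95% CIs and p-values will be provided for VAS (mm) score in Table 14.2.4.1.2") follow the same pattern. Appendix 1 lists the matching displays, for example "Statistical Analysis of Change from Baseline in Schiff Sensitivity Score Over Time (MMRM"), together with the raw SAS output for each MMRM. No text or title mentions a ratio or percentage difference.

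**The concern.** Protocol 2.1 says the trial is needed because the Chinese guidelines require a study in a local population, so a threshold from those guidelines is not incidental. The plan shows that the threshold is met only by dividing expected means. A trial can be significant on Schiff and still show an observed relative difference below 15%, and the 92.65% says nothing about the chance of reaching 15%. With no planned ratio, no interval for it and no statement of how the three measures will be read, the sponsor could appear free to choose the measure, the denominator, or the estimate rather than a confidence limit after seeing the data. At stake would be the credibility of any later statement that the guideline threshold was met.

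**Working it through.** **Inputs.** From Protocol 12.1: difference d = 0.3, SD = 0.6, n = 94 per arm, two-sided 5%. The documents give the negative-control change c only as below 2, so c is assumed over 0.5 to 1.99. Changes are expressed as sizes of reduction. The guideline's own formula is not in the documents, so the relative difference is taken as (test change − control change) / control change.

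**The plan's figures.** SE of the difference = 0.6 × √(2/94) = 0.0875, and the noncentrality is 0.3/0.0875 = 3.43. On 186 df the noncentral t gives power of 92.65%, as stated. The 15% statement is d/c = 0.3/2 = 15%, so the ratio exceeds 15% whenever c < 2. Both figures are right.

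**Where significance and 15% part company.** The smallest significant difference is 1.973 × 0.0875 = 0.173. That equals 15% of c = 0.173/0.15 = 1.15. Below an observed control change of about 1.15, a significant Schiff result already carries a ratio above 15%. Above it, it need not.

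**How often.** The observed ratio reaches 15% when T − 1.15C ≥ 0, where T and C are the observed arm means. This quantity has mean 0.3 − 0.15c and SE 0.6 × √((1 + 1.15²)/94) = 0.0943. For c = 1.5 that is 0.075/0.0943 = 0.80, or 79%. The joint event with significance was simulated (2,000,000 draws of the arm means and pooled SD). The Fieller 95% limits R for T/C, evaluated at the planned means, solve (T − R·C)² = t² × (0.36/94) × (1 + R²); subtracting 1 gives the relative difference. Arms are treated as independent, with no covariate adjustment.

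| Control change c | Expected ratio 0.3/c | P(observed ratio ≥ 15%) | P(significant, ratio < 15%) | Lower Fieller limit |
|---|---|---|---|---|
| 0.5 | 60% | 99% | about 0% | 21.6% |
| 0.75 | 40% | 98% | about 0% | 15.2% |
| 1.0 | 30% | 94% | 0.1% | 11.7% |
| 1.25 | 24% | 88% | 4.3% | 9.5% |
| 1.5 | 20% | 79% | 14% | 8.0% |
| 1.99 | 15.1% | 51% | 42% | 6.1% |

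These figures are for Schiff alone. The requirement needs only one of the three measures, so for a true difference of 0.3 the fourth column overstates the chance of succeeding and yet missing 15% on every measure. It is not a ceiling for smaller effects: at d = 0.25 and c = 1.5 it is 21%.

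**What the planned output already supplies.** The point ratio is the LS mean difference divided by the negative-control LS mean change, and both are planned for each measure (Protocol 12.3.2; SAP 4.4.1.2, 4.4.2.2.1, 4.4.2.3.1). The model, population and visit are fixed in advance. An approximate interval can also be built. The per-arm and difference CIs give the three standard errors, and the covariance of the two LS means follows as (SE_T² + SE_C² − SE_D²)/2.

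**The case for a change.** The best case for a change is that the requirement is one the sponsor itself cites, that it bears on the purpose of the trial, and that one derived row in three tables would cost almost nothing. Being able to calculate a ratio by hand is not the same as pre-specifying it. Nothing says which measure counts, or whether 15% is compared with the estimate or with a confidence limit. Control changes above 1.15 cannot be ruled out, because Protocol 4.2 says placebo effects are frequent in these studies and test teeth start at Schiff 2 or 3.

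It is true that the ratio is not tabulated and that its reading is not written down. The rest is weaker.

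- **Estimate or limit.** This depends on a guideline that is not in the documents. Their wording describes a comparison of mean changes and mentions no confidence limit for the 15%. Nor does the choice always matter: at control changes of 0.5 and 0.75 the lower limit also exceeds 15%.
- **The power statement.** No sentence presents 92.65% as power for the 15%. It is tied to an effect size of 0.5 and a t-test, and the 15% remark is framed as following from assumptions, with its condition in brackets.
- **Room for choice after unblinding.** The numerator, the natural denominator, the model and the population are already set. What remains open is how an external rule is interpreted.
- **The extra row has its own limits.** The tactile ratio would depend on the 90 g assigned to readings above 80 g (SAP 4.4.2.2). For any measure, an MMRM ratio could sit beside a Van Elteren test that takes precedence under strong violations of the model assumptions.

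**Conclusion.** No change is needed. Followed as written, the plan gives a valid test of its stated success criterion and reports the adjusted means from which anyone can compute the relative difference for Schiff, tactile threshold and VAS. The sample-size statement is arithmetically correct and properly conditional. What is missing is a reporting detail for a benchmark that sits outside the trial's objectives, and an analyst preparing the guideline argument would fill it with one division.

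Significance and the 15% threshold can disagree on Schiff: from about 0% of trials at control changes up to 0.75, through 14% at 1.5, to 42% at 1.99. This assumes a true difference of 0.3, SD 0.6, 94 per arm and the ratio as defined above; a smaller true difference raises the figures at the larger control changes. A disagreement would be visible from the planned tables and would leave the primary conclusion intact. Showing the Week 12 ratio with a Fieller interval as a descriptive row is a reasonable option for the report, but no planned conclusion depends on it.
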